9.7.1 Primary analysis

The general statistical considerations described above will be applied to quantitative and qualitative variables. The number of missing data will be indicated. Missing values are expected to be few and distributed at random. Since there is no applicable method unanimously accepted, there will be no replacement or imputation of missing data.²⁴ Confidence interval of 95% will be evaluated for endpoint variables.

For each question associated with an outcome included in the objectives, a criterion will be applied to separate participants with the correct and desirable answers (or at least one correct and desirable answer as a response if the corresponding question allows multiple answers/true-false or is an open-ended question). These proportions of correct and desirable answers to each question will be expressed for HCPs/vaccinees who answer that question. Analysis for the survey will be performed for HCPs and vaccinees separately for the endpoints described below:

Primary endpoints

- Awareness of the UK (STAMARIL®) yellow fever pre-vaccination checklist will be assessed through the percentage of qualified HCPs who are aware of the checklist.
- Utilisation of any standardised yellow fever pre-vaccination checklist(s) (UK (STAMARIL®) yellow fever pre-vaccination checklist or NaTHNaC/PHS yellow fever pre-vaccination checklist) will be assessed through the percentage of qualified HCPs who frequently or always use any standardised yellow fever pre-vaccination checklist(s).
- **Distribution of the STAMARIL**® **PIL by qualified HCPs to vaccinees** will be assessed through the percentage of qualified HCPs who frequently or always distribute it among yellow fever vaccinees.

- Knowledge and understanding of the key safety messages will be assessed through the percentage of qualified HCPs who provide desirable responses to the related question on key safety messages associated with yellow fever vaccination in any standardised yellow fever pre-vaccination checklist(s).
- Receipt of the STAMARIL® PIL will be assessed through the percentage of vaccinees who receive the PIL.

Secondary endpoint: None Assessment of success

In each survey, the proportion of correct or desirable responses across all questions related to the evaluation of the primary objectives of the surveys will be considered to assess the success.

The questions considered as complementary will not be included in the assessment of success. The details of the assessment of the success for each survey and each objective is described in Annex 6.

Success at the HCP/vaccinee level will be defined for each primary objective based on the number of sub-questions related to that objective being completed with desirable responses. A HCP/vaccinee will be successful in each objective (except knowledge and understanding for HCPs) if all related questions, including sub-questions, will be completed with desirable responses (Annex 6). An HCP will be successful for knowledge and understanding of any standardised yellow fever pre-vaccination checklist(s), if at least 80% of the related questions, including sub-questions, are completed with desirable responses.

A threshold of 80% successful HCPs or vaccinees on each of the primary outcomes would be considered appropriate for assessing the effectiveness of an aRMM.

It should be noted that the selection of this threshold for success is subjective and not based on *a priori* knowledge, experience, or established scientific criteria in the education or risk communication or evaluation literature. If additional information from published literature becomes available at the time of reporting, then the results will be discussed in the context of this new information. The methods of reporting and analysis of results obtained will be done as already described in this protocol and will be further detailed in the statistical analysis plan (SAP).

Description of characteristics of HCPs with desirable/undesirable responses

The charactertistics of HCPs with desirable and undesirable responses to questions related to each outcome will be described using all available and relevant participant information collected in the survey (i.e. region, HCP profession, gender, age range, duration of practice, type of setting, years of professional experience and experience with STAMARIL®). This will be further detailed in the SAP.

Description of characteristics of vaccinees with desirable/undesirable responses

The characteristics of vaccinees with desirable and undesirable responses to questions related to each outcome will be described using all available and relevant participant information collected

in the survey (i.e., age range, region, gender, and education level). This will be further detailed in the SAP.

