To evaluate knowledge and understanding The proportion of qualified HCPs who of the key safety messages associated with provide desirable responses for each yellow fever vaccination in any question related to knowledge and standardised yellow fever pre-vaccination understanding of key safety messages. checklist(s) among qualified HCPs of Success indicator for knowledge and designated authorised YFVCs in the UK. understanding: If ≥80% of qualified HCPs are successful (a qualified HCP is considered successful when he/she provides at least 80% of desirable responses to questions related to knowledge and understanding). To verify the receipt of the STAMARIL® a. The proportion of yellow fever vaccinees who receive the STAMARIL® PIL by yellow fever vaccinees at the time they get vaccination consultation in the UK. PIL Success indicator for receipt of STAMARIL® PIL: If >80% of vaccinees are successful (a vaccinee is considered successful when he/she receives the STAMARIL® PIL). Secondary objective: None

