Annex 6 Assessment of success

6.1 Assessment of success (HCP questionnaire)

Objectives	Questions	Is the question included in the assessment of success? (Yes/No)	Definition of desirably/correctly answered question	Assessment of success
	Q1. According to your knowledge about the conditions of use for STAMARIL® (yellow fever vaccine), which of the following statements do you agree/disagree with? Please select all options that apply	Yes	Question completed correctly [5 points (3 True and 2 False)]	
Knowledge and Understanding (5 questions)	Q2. According to your knowledge about the risks associated with STAMARIL® (yellow fever vaccine) administration, which of the following statements do you agree/disagree with? Please select all options that apply	Yes	Question completed correctly [4 points (2 True and 2 False)]	An HCP is considered successful for knowledge and understanding when he/she provides at least 22 out of 27 (80%) correct/desirable
(5 questions)	Q3. According to your knowledge about STAMARIL® (yellow fever vaccine), this vaccine is contraindicated in the following circumstances: Please select all options that apply	Yes	Question completed correctly [10 points (7 True and 3 False)]	responses. Success for knowledge if ≥80% of HCPs are successful.
	Q4. According to your knowledge about the risks associated with STAMARIL® (yellow fever vaccine) administration, which of the following are the possible side effects of this vaccine? Please select all options that apply.	Yes	Question completed correctly [5 points (4 True and 1 False)]	

Objectives	Questions	Is the question included in the assessment of success? (Yes/No)	Definition of desirably/correctly answered question	Assessment of success	
	Q5. According to your knowledge about STAMARIL® (yellow fever vaccine) administration to pregnant/breastfeeding women, which of the following statements do you agree/disagree with? Please select all options that apply	Yes	Question completed correctly [3 points (2 True and 1 False)]		
Awareness (2	Q6. Please select the option that best describes your experience with the standardised yellow fever pre-vaccination checklist(s).	Yes	Question completed desirably [Answers: 1 or 2 are desirable]	An HCP is considered successful for awareness when he/she is aware of the UK (STAMARIL®) yellow	

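### Section 9.7.1 counts a true/false knowledge question as correct when a single item is right, which conflicts with the item scoring in Annex 6.1 and leaves the per-question knowledge endpoint barely able to discriminate

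*Protocol*

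**What the plan says.** Protocol section 9.7.1 applies a criterion to every question tied to an outcome in the objectives. For a question with several answers, a true/false format or free text, the criterion is "or at least one correct and desirable answer as a response if the corresponding question allows multiple answers/true-false or is an open-ended question". The result is reported question by question: "These proportions of correct and desirable answers to each question will be expressed for HCPs/vaccinees who answer that question".

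Table 1 in section 8 (its columns are interleaved in the text as read) makes the endpoint for objective 2 the proportion of qualified HCPs giving desirable responses to each knowledge question. Its success indicator is separate. An HCP succeeds when "he/she provides at least 80% of desirable responses to questions related to knowledge and understanding", and the objective is met if at least 80% of HCPs succeed.

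Annex 6.1 sets out the scoring of the five knowledge questions. Q1 is "Question completed correctly [5 points (3 True and 2 False", Q2 is "Question completed correctly [4 points (2 True and 2 False" and Q3, on contraindications, is "Question completed correctly [10 points (7 True and 3 False". Q4 carries 5 points (4 true, 1 false) and Q5 carries 3 (2 true, 1 false). An HCP is successful for "knowledge and understanding when he/she provides at least 22 out of 27 (80%) correct/desirable" responses.

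Section 9.7.1 also plans to describe the characteristics of HCPs with desirable and undesirable responses to the questions for each outcome.

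**The concern.** The protocol holds two definitions of a correctly answered knowledge question. Annex 6.1 awards a point per item and speaks of completing the question correctly. Section 9.7.1 accepts one right item. On Q3 an HCP could be wrong on nine of ten contraindication items and still be counted as correct.

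Two planned outputs depend on this definition: the per-question proportions that Table 1 names as the objective 2 endpoint, and the comparison of HCPs with desirable and undesirable responses. If almost everyone is classed as correct whatever they know, the first says little and the second has almost nobody in its undesirable group. Contraindication knowledge matters here because section 7 traces the checklist to two fatal reactions after unapproved use.

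**Working it through.** **Inputs.** Items per question k = 5, 4, 10, 5, 3 for Q1 to Q5, and items whose right answer is true = 3, 2, 7, 4, 2 (Annex 6.1). The pass mark is 22 of 27 (Annex 6.1). The relaxed rule comes from section 9.7.1.

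**The plan's own figure.** 5 + 4 + 10 + 5 + 3 = 27, and 0.8 × 27 = 21.6, which rounds up to 22. 22/27 = 81.5%, while 21/27 = 77.8% falls short. The Annex 6.1 cut-off is reproduced.

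**Checks that need no guessing assumption.**
- Answering true to everything gives 3 + 2 + 7 + 4 + 2 = 18 of 27. That fails Annex 6.1, but every question has at least one right item, so all five count as correct under 9.7.1.
- Answering false to everything gives 27 − 18 = 9 of 27, again with at least one right item in every question.
- The lowest total compatible with being correct on all five is one item each, 5 of 27.

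**Guessing.** Let p be the chance of a right answer on each item, independent across items. The questionnaire is a stand-alone document and is not shown, so p is an assumption. A don't-know option, if there is one, would lower it.
- At least one item right: 1 − (1 − p)^k
- All items right: p^k

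Percentage of HCPs counted as correct under the rule in 9.7.1:

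| p | Q1 (5) | Q2 (4) | Q3 (10) | Q4 (5) | Q5 (3) |
|---|---|---|---|---|---|
| 0.3 | 83.2 | 76.0 | 97.2 | 83.2 | 65.7 |
| 0.4 | 92.2 | 87.0 | 99.4 | 92.2 | 78.4 |
| 0.5 | 96.9 | 93.8 | 99.9 | 96.9 | 87.5 |
| 0.6 | 99.0 | 97.4 | 99.99 | 99.0 | 93.6 |
| 0.8 | 99.97 | 99.8 | 100.0 | 99.97 | 99.2 |

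For example, Q1 at p = 0.5 is 1 − 0.5^5 = 0.969 and Q3 is 1 − 0.5^10 = 0.999.

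**Discrimination.** Moving from coin-flipping (p = 0.5) to getting 80% of items right (p = 0.8) shifts Q1 by about 3 percentage points and Q3 by about 0.1. If all items had to be right, Q1 would move from 3.1% to 32.8% and Q3 from 0.1% to 10.7%. At p = 0.5 the all-items rule gives 3.1%, 6.3%, 0.1%, 3.1% and 12.5% for Q1 to Q5.

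**Success indicator.** The probability of at least 22 of 27 is 0.0008 at p = 0.5 and 0.54 at p = 0.8. That rule discriminates well and does not use the relaxed criterion.

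**The case against.** The strongest defence is that the effectiveness conclusion is protected. The only pass/fail rule for objective 2 counts sub-questions and is fixed at 22 of 27 items in Annex 6.1, and the relaxed wording does not enter it. This stands. A reader might infer that guessers could pass the knowledge objective, for instance by getting four of five questions right. The protocol contains no four-of-five rule.

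The second defence is that section 9.7 (general statistical considerations) plans the frequency of each option for multiple-choice questions. A reader might infer from 9.7.1 that a gap on the contraindication items would go unseen, but those tables may show a weak single item. This also stands. They do not repair the named endpoint, though: the same section sets aside combinations of answers, so they would not show how many Q3 items each HCP got right.

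Third, it is tempting to say that the per-question endpoint cannot fail. No threshold is set for any single question, so there is nothing to pass or fail. The fault is lack of information, not a guaranteed pass. Likewise, 22 of 27 can be reached with five Q3 items wrong (27 − 5 = 22), but that is a property of the total score and no fault of 9.7.1.

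Finally, the wording might be called a generic phrase that the SAP will refine. But it names true/false questions expressly, and section 9.7.1 says the analysis will follow what the protocol already describes, with further detail in the SAP. A SAP faithful to the protocol would carry the rule forward.

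**Conclusion.** The point holds for the per-question knowledge results and for the desirable/undesirable description, and goes no further. As written, the correctness rule in section 9.7.1 contradicts Annex 6.1 and makes the Table 1 per-question endpoint nearly uninformative.

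The contradiction and the all-true example (18 of 27, yet correct on all five) rest on the documents alone. The guessing rates of 87.5% to 99.9% rest on independent answers with p = 0.5. The spread across questions is 65.7% to 97.2% at p = 0.3 and 93.6% to 99.99% at p = 0.6. Rates close to 100% therefore fit the longer questions better than the three-item Q5. The 22-of-27 success indicator stands.

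**What to change.** In section 9.7.1, remove the one-right-answer criterion for Q1 to Q5 and align the text with Annex 6.1. Report the percentage correct for each item, and for each question a summary based on item points, such as mean points or the percentage with all items right. Use that same definition when HCPs with desirable and undesirable responses are described. Keep 22 of 27 for the success indicator. Limit the one-right-answer wording to select-all questions with a single desired option, such as Q7.

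The cost is a change of wording and the matching derivations in the SAP, with no new data. The per-question figures will look less favourable.

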8 RESEARCH QUESTION AND OBJECTIVES

The aim of the current study is to examine the effectiveness of the UK (STAMARIL®) yellow fever pre-vaccination checklist among the qualified HCPs of designated authorised YFVCs and of the STAMARIL® PIL among the yellow fever vaccinees in the UK by conducting a survey in this population.

The objectives and endpoints of this study are presented in **Table 1**.

Table 1 Objectives and endpoints

Objectives	Endpoints				
Primary objectives					
To measure: a. Awareness of the UK (STAMARIL®) yellow fever pre-vaccination checklist by qualified HCPs of designated authorised YFVCs in the UK.	a. The proportion of qualified HCPs who are aware of the UK (STAMARIL®) yellow fever pre-vaccination checklist. Success indicator for awareness: if ≥80% of qualified HCPs are successful (a qualified HCP is considered successful when he/she is aware of the UK (STAMARIL®) yellow fever pre-vaccination checklist).				
b. Utilisation of any standardised yellow fever pre-vaccination checklist(s) by qualified HCPs of designated authorised YFVCs in the UK.	 b. The proportion of qualified HCPs who frequently or always use one or both the standardised yellow fever prevaccination checklists. Success indicator for utilisation: if ≥80% of qualified HCPs are successful (a qualified HCP is considered successful when he/she frequently or always uses at least one of the standardised yellow fever pre-vaccination checklists). 				
c. Distribution of the STAMARIL® PIL by qualified HCPs of designated authorised YFVCs to yellow fever vaccinees in the UK.	c. The proportion of HCPs who frequently or always distribute the STAMARIL® PIL to yellow fever vaccinees in the UK. Success indicator for distribution of the STAMARIL® PIL by HCPs: if ≥80% of qualified HCPs are successful (a qualified HCP is considered successful when he/she is frequently or always distributes the STAMARIL® PIL).				

Property of the Sanofi Group - strictly confidential

31-May-2023

Version number: 3.0

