9.8 QUALITY CONTROL

9.8.1 Data collection, validation, and data quality control

Data will be collected using a web/paper-administered questionnaire to HCPs and vaccinees. The survey will be conducted according to the Standard Operating Procedures (SOPs) of IQVIA Primary Intelligence and IQVIA Real World Evidence Solutions.

Data from the web-based questionnaire will be collected using an electronic data capture (EDC) system developed following a full validation process. Similarly, data from the paper questionnaire will be entered into the EDC and thereafter validated along with the data collected via the web-based questionnaire. A rigorous System Development Life Cycle that complies with IQVIA Primary Intelligence information technology SOPs will be used for validation. The programmed survey will be tested and validated in accordance with IQVIA SOPs, which cover validation for all clinical and risk management-related applications. The internet-based repository will be used to store survey data and other relevant programme information. Questions are programmed to ensure that they are asked in the appropriate sequence. Skip patterns are clearly indicated. Respondents cannot go back to a question once the question has been answered and cannot skip ahead without answering the previous question. Response options presented in a list are randomised to minimise positional bias. Programming will be reviewed by Quality Control and simulated users (User Testing) prior to implementation. Collected data will be entered and stored in a database specific to the survey. The HCP-identifying information will be stored separately from survey data.

Data will be checked in terms of consistency before data analysis:

- Removal of duplicates (if required)
- Data labelling and data formatting
- Range and consistency checks for each variable to identify potential non-admissible values
- Cross-check the consistency of data for related variables (if feasible).

The number of variables with missing values will be indicated. Missing values are excluded from the calculation of percentages. The study database will be locked once validated.

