questions)	Q7. Please select which of the following standardised yellow fever pre-vaccination checklist(s) you have received or are aware about: Please select all options that apply	Yes	Question completed desirably [Answer: 1 is desirable]	fever pre-vaccination checklist Success for awareness if ≥80% of HCPs are successful.	
	Q8. Please select the option that best describes your experience with the use of the yellow fever pre-vaccination (STAMARIL®) checklist issued by the Medicines and Healthcare products Regulatory Agency (MHRA)	Yes	Question completed desirably [Answers: 1 or 2 are desirable]	An HCP is considered successful for utilization when he/she utilizes either the UK (STAMARIL®) yellow fever pre-vaccination	
Utilization (7 questions)	Q9. Please select the option(s) that best describes why you never/rarely/sometimes use the yellow fever pre-vaccination (STAMARIL®) checklist issued by the Medicines and Healthcare products Regulatory Agency (MHRA): Please select all options that apply	No	Complementary question	yellow fever pre-vaccination checklist or traveller checklist Success for utilization if ≥80% of HCPs are successful.	

Page 78

Objectives	Questions	Is the question included in the assessment of success? (Yes/No)	Definition of desirably/correctly answered question	Assessment of success
	Q10. Please select the option(s) that best describes the challenges you face while using the yellow fever pre-vaccination (STAMARIL®) checklist issued by the Medicines and Healthcare products Regulatory Agency (MHRA): Please select all options that apply	No	Complementary question	
	Q11.Please select the option that best describes your experience with the use of the yellow fever pre-vaccination checklist (i.e. traveller checklist) issued by the National Travel Health Network and Centre (NaTHNaC) and Public Health Scotland (PHS)	No	Question completed desirably [Answers: 1 or 2 are desirable]	
	Q12. Please select the option(s) that best describes why you never/rarely/sometimes use the yellow fever pre-vaccination checklist (i.e., traveller checklist) issued by the National Travel Health Network and Centre (NaTHNaC) and Public Health Scotland (PHS): Please select all options that apply	No	Complementary question	

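### Utilisation should be met by frequent use of either checklist, but the Q11 inclusion flag in Annex 6.1 and the all-questions rule in section 9.7.1 contradict this

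*Protocol*

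**What the plan says.** The protocol states the utilisation rule in three places, each time as use of at least one checklist.

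- Section 8, Table 1: an HCP is successful when "he/she frequently or always uses at least one of the standardised yellow fever pre-vaccination checklists".
- Section 9.7.1, primary endpoints: the "percentage of qualified HCPs who frequently or always use any standardised yellow fever pre-vaccination checklist(s").
- Annex 6.1, last column: "An HCP is considered successful for utilization when he/she utilizes either the UK (STAMARIL®) yellow fever pre-vaccination" checklist or the traveller checklist. No frequency is given here.

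Two other instructions bear on the same endpoint.

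- Annex 6.1 has a Yes/No column for whether a question enters the assessment of success. Q8, on the UK checklist, is *Yes*. The traveller-checklist item ("Q11.Please select the option that best describes your experience with the use of the yellow fever pre-vaccination checklist (i.e. traveller checklist") is *No*, although its row defines answers 1 or 2 as desirable.
- Section 9.7.1, assessment of success: an HCP or vaccinee "will be successful in each objective (except knowledge and understanding for HCPs) if all related questions, including sub-questions, will be completed with desirable responses". Only complementary questions are left out. In Annex 6.1, Q9, Q10, Q12, Q13 and Q14 are labelled complementary and Q11 is not.

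The indicator succeeds if at least 80% of HCPs are successful.

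**The concern.** The respondent-level derivation depends on which instruction is followed. Under the Annex 6.1 flag, only Q8 counts. Under the all-questions sentence with Q11 counted, both Q8 and Q11 must be desirable. Neither is the rule in Table 1.

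The HCPs affected are those who use the traveller checklist regularly but not the UK checklist. Table 1 counts them as successes; the other two derivations count them as failures. They may be numerous, because section 7 reports that more than 90% of centres in England, Wales and Northern Ireland used a traveller checklist in 2020. At stake is the pass or fail verdict on a primary endpoint.

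**Working it through.** **Inputs.** The threshold is 80% (Table 1, section 9.7.1). The minimum HCP sample is 200 (section 9.5.1). Q11 is set at p11 = 0.90, taken from the centre-level figure in section 7 as a stand-in for a desirable Q11 answer. The Q8 share p8 is not in the protocol, so it is varied.

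**The plan's own figure.** n = P(1 − P) × 1.96² / e². With P = 0.5 and e = 0.07, n = 0.25 × 3.8416 / 0.0049 = 196.0. This matches the cell in Table 2, and the target of 200 rounds it up. The figure is not in dispute; it supplies the sample size used below.

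**Formulas.**
- Q8 only: p8.
- Q8 and Q11: p8 × p11 if independent; in general between max(0, p8 + p11 − 1) and min(p8, p11).
- Q8 or Q11: p8 + p11 − p8 × p11 if independent; in general between max(p8, p11) and min(1, p8 + p11).
- Chance of passing: binomial probability of at least 160 successes in 200 (160/200 = 80%), with the joint shares taken under independence.

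**Results with p11 = 0.90** (bounds without independence in brackets):

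| Q8 share (assumed) | Q8 only | Q8 and Q11 | Q8 or Q11 | Chance of passing: Q8 only / and / or |
|---|---|---|---|---|
| 50% | 50% | 45% (40–50) | 95% (90–100) | 0.00 / 0.00 / 1.00 |
| 70% | 70% | 63% (60–70) | 97% (90–100) | 0.001 / 0.00 / 1.00 |
| 80% | 80% | 72% (70–80) | 98% (90–100) | 0.54 / 0.006 / 1.00 |
| 85% | 85% | 76.5% (75–85) | 98.5% (90–100) | 0.98 / 0.14 / 1.00 |
| 90% | 90% | 81% (80–90) | 99% (90–100) | 1.00 / 0.68 / 1.00 |
| 95% | 95% | 85.5% (85–90) | 99.5% (95–100) | 1.00 / 0.99 / 1.00 |

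**Reading the table.** The either-checklist share is never below p11, so at p11 = 0.90 it passes whatever the Q8 share. Q8 only falls short whenever p8 is below 80%, and the joint rule can never exceed p8. So below 80% the either rule passes and both alternatives fail, with no independence assumption. At a true Q8 share of 80% or more, the either rule and Q8 only agree, apart from sampling error close to 80%. The joint rule may still fail: under independence it needs 0.90 × p8 ≥ 0.80, so p8 ≥ 0.80 / 0.90 = 88.9%.

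**How far this depends on the 90%.** The either rule is at least max(p8, p11), so the same reversal holds for any p11 of 80% or more. If both shares are below 80%, the result depends on how far users of the two checklists overlap.

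**The case against.** The best reply is that only one utilisation rule is written out, and it is the either-checklist rule. It stands in Table 1, in the endpoint text of section 9.7.1 and in the success column of Annex 6.1. It also fits objective 1b and the definition of the standardised checklists in section 7. The amendment summary confirms the intent by saying that listing Q11 as complementary was an error. The all-questions sentence is generic and refers to Annex 6 for detail. This is right as far as it goes. A reader might infer that the protocol sets out three competing utilisation rules, and it does not: Q8-only and Q8-and-Q11 result from applying the generic sentence with Q11 left out or counted. But deferring to Annex 6 does not settle the matter, because the Annex 6.1 flag conflicts with the success text beside it. The SAP, which is not shown, is meant to detail methods already described in the protocol, so it cannot follow all of these instructions at once.

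It is also fair that the analyses are descriptive, that the protocol calls the 80% threshold subjective, and that the size shown above is illustrative. These points lower the severity but leave the contradiction in place.

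A reader might go further and infer that HCPs unaware of a checklist drop out of the denominator. Proportions "will be expressed for HCPs/vaccinees who answer that question", and for the web questionnaire "Skip patterns are clearly indicated". The documents do not support that inference. The HCP questionnaire is a separate document, and nothing shows that Q8 or Q11 is asked only of aware HCPs. Q9 and Q12 ask why an HCP never, rarely or sometimes uses each checklist, which suggests that non-users are asked. The sentence on answerers governs per-question proportions, while the endpoint is defined on qualified HCPs. No denominator bias is claimed here.

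**Conclusion.** The contradiction is real and lies in current text. The intended rule is frequent or constant use of at least one checklist (Q8 or Q11). The Annex 6.1 flag for Q11 reduces it to Q8 alone; the unexempted sentence in section 9.7.1 turns it into Q8 and Q11 if Q11 is counted. Either misreading can only lower the indicator. With traveller-checklist use at about 90%, the verdict reverses for any Q8 share below 80%; at or above 80% only the joint rule may still fail.

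The size rests on two assumptions: a Q8 share that the protocol does not give, and a 2020 centre-level figure, excluding Scotland, standing in for individual HCPs answering frequently or always. The direction does not depend on the exact values.

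This should be fixed. It falls short of a critical defect because the intended rule is stated clearly and repeatedly elsewhere.

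**What to change.** Make three edits to the protocol.

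1. In Annex 6.1, change the inclusion flag for Q11 from *No* to *Yes*.
2. In section 9.7.1, add utilisation to the exception to the all-questions rule: *for utilisation, an HCP is successful if Q8 or Q11 is answered 1 or 2*.
3. In the Annex 6.1 success column, replace the bare reference to using either checklist with *frequently or always utilises at least one*, to agree with Table 1.

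The cost is one table cell, one clause, one wording change and the matching derivation in the SAP. Q8 and Q11 are both already in the questionnaire, so no new data are needed.
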